Visits done between 14 and 28 days after the calculated visit date will be considered a protocol deviation. Visits outside of the +28 day window will not be scheduled and that visit will be considered missing for that patient. The fasting lipid panel blood draw will be done at the time of study visit or within a +/- 10 day window. To limit potential bias, participants, their healthcare providers, and the prevention nurse delivering the education modules will be blinded to the in-office BP outcome measure unless a safety threshold is exceeded (systolic BP <90 or >180mmHg). BP may be re-checked separately as part of routine care.

Control participants will be encouraged to maintain participation in the study in order to minimize differential loss-to-follow-up between intervention and control group that would jeopardize the validity of study findings. As recommended by the design teams, we will conduct semi-annual participant engagement parties (in January and July) that will consist of a meal, healthy lifestyle education and games. We will report enrollment and other study related news to participants. All participants—both intervention and control—will be invited to these events. As an additional incentive, control participants will receive a BP monitor and instructions about its use after completion of the final 12-month trial visit.

EXTRA-CVD intervention: Participants randomized to the intervention will meet with the site prevention nurse on the day of enrollment. With nurse assistance, the participant will complete an initial ASCVD risk assessment using the ACC/AHA risk calculator and a risk visualization tool available at <https://statindecisionaid.mayoclinic.org/>. This exercise will help establish rapport between the participant and the nurse, and will help identify potential targets for intervention. The nurse will conduct a baseline medication assessment, including participant's knowledge of the purpose and side effects of each BP or cholesterol medication and current or potential adherence strategies.

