Our study team is extremely prudent in keeping subject data secure and confidential. The control of access to study databases will be managed centrally by IT systems at each clinic site through user passwords linked to appropriate access privileges. This protects forms from unauthorized view and modifications as well as inadvertent loss or damage. Database servers at each clinic site are secured by a firewall as well as through controlled physical access. We will use a REDCap database (projectredcap.org) to store all study data. REDCap has many security protection features that ensure that each person accessing the database has the proper authority to perform the functions he or she requests of the data management system. Within the secondary SAS databases, UNIX group access control will be used for maintaining similar security. University Hospitals REDCap IT will ensure that only IRB-approved individuals on the study team will have access to individually identifiable information about human subjects. This will include the PIs, co-investigators, project coordinator, statisticians, database/programming team, and research assistants. Some of the data above will be accessed from information already collected as part of usual care. All additional data from subjects will be specifically collected for the proposed research project and not a part of clinical care.

Potential risks

Loss of confidentiality. The risks associated with gathering mixed methods data from participants by properly trained and supervised research assistants and technical staff is low and include risks of loss of privacy and psychological distress.

Detection of clinically significant problems: Although not caused by study participation, it is possible that clinically significant problems will be detected by study staff. Subjects entering the

study will have a history of hypertension and hyperlipidemia so we expect to see abnormal systolic and diastolic values, as well as abnormal lipid values. All values that reach a safety threshold (<90 or >180 systolic BP, <40 or >110 diastolic BP) will be reported to the subjects' care provider.

Kidney disease and electrolyte imbalances: Some of the blood pressure agents used in the nurse-managed protocols may cause acute kidney injury and electrolyte imbalances. Subjects with underlying kidney disease at baseline will be at higher risk.

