Blood Pressure: All participants will have a high risk for CVD, and thus many will be prescribed hypertension medications by their health care provider at the outset of the study. It is likely that as a result of increased monitoring, we will detect more episodes of abnormal BP values. Because of potential high and low BP values, subjects in the intervention arm may have their current hypertension regimen adjusted. Safety monitoring of BP will occur in the context of home BP monitoring as well as BP measurement during data collection visits. An average SBP at any study visit or during home blood pressure monitoring > 180 mm Hg and/or diastolic is > 110 mm Hg will be considered an alert value and will trigger assessment by the clinician. Furthermore, an average at any study visit or during a home blood pressure monitoring that is < 90 systolic or < 40 diastolic would also be considered an alert value and would trigger an assessment by a clinician. Participants who have an alert reading at home will be asked to contact the clinician directly so that she/he can assess for any cardiovascular symptoms.

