Participants who have an alert BP reading during study visits will be directly assessed for cardiovascular symptoms during the visit. Once an alert value has been confirmed the participant will be triaged according to follow-up recommendations from Joint National Committee Recommendations (JNC 8). Participants will have access to their regular providers as well as the following study investigators designated as the clinical contact for each site: [name] (infectious disease physician and HIV clinic director; UH Special Immunology Unit), [name] (infectious disease physician and HIV clinic director; MetroHealth Medical Center) and [name] (infectious disease physician; Duke Health). If at any time, participants have symptoms of acute end organ damage (i.e. current chest pain, dyspnea at rest, new onset of blurry vision, or new neurological deficits consistent with a stroke) in the context of an elevated BP measurement (SBP > 180 , and/or DBP > 110), participants will be asked to contact the clinician and will be advised and assisted in seeking emergency medical care. For participants in the intervention group whose average SBP > 180 and DBP > 110 or SBP < 90 or DBP < 40 but are without acute symptoms, the participant's primary provider will be notified and medications will be changed as deemed appropriate by the study team. Follow up contact with the study staff will occur within one week. All abnormal blood pressure results will be communicated to the clinic director at each site who will be an integral part of triage and ensuring follow up. Any change in medication management or observation of an alert value will be communicated from the nurse as soon as possible. The prevention nurse will then generate a note to be entered into the electronic medical record and will communicate directly with the subject's PCP. The research nurses will be integrated parts of their respective health clinic.

Medication adverse effects, including kidney and electrolyte imbalances: All participants who are prescribed a clinically indicated new medication according the nurse-managed protocol will have that medication prescribed by the participant's usual health care provider, who will take primary responsibility for counseling the patient about side-effects and ordering follow-up laboratories. In addition, each participant will be counseled by the prevention nurse about

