Sharing of Results with Research Participants:

As an implementation study that aims to improve clinical care of patients, any relevant clinical data will be shared with patient participants and/or their clinical care team as they would typically be shared through the course of clinical care. This primarily consists of home blood pressure data (intervention arm) and lipid panels, which will result in the electronic health record for both intervention and control participants. Because of the need to maintain the integrity of

the control condition, the prevention nurse will not directly communicate blood pressure or cholesterol results to the control group participants or their providers unless they exceed the safety thresholds defined above. Results of surveys acquired for research purposes only will not be shared directly with participants. At the end of the trial, final aggregate primary results will be disseminated to participants through presentations to local community advisory boards and/or clinic staff at the local sites.

Data Safety Monitoring:

All elements of the data and safety monitoring plan will be reviewed by the IRB at UH and provided to the NIH institute overseeing the project. The study PIs—[name], [name], and [name] together with the UH IRB PI [name]—will share responsibility for monitoring risks to human subjects and implementation of the monitoring plan. The project will utilize existing medical referral sources and physicians knowledgeable about HIV to address any physical risks that might arise. Serious adverse events will be reported promptly to the institution's IRB and project officer of the funding source. Monitoring procedures and reporting and action plans for data and safety-related risks are described below. The Data and Safety Monitoring Plan includes the following components which will be addressed individually below:

- Regulatory Issues
- Data Safety and Monitoring Board
- Data Validity/Integrity
- Protocol Compliance
- Termination for Significant Risk

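### Aim 2 trial: the rule that lifts blinding of the in-office BP has systolic limits only, while the safety thresholds elsewhere in the protocol also include diastolic BP below 40 or above 110 mmHg

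*Combined protocol and SAP*

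**What the plan says.** Four places in the protocol set or use the BP safety limits.

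- **Section 8, Aim 2 Procedures, study assessments.** The assessments are defined for both arms. The blinding sentence begins "To limit potential bias, participants, their healthcare providers, and the prevention nurse delivering the education modules will be blinded", and those parties are "blinded to the in-office BP outcome measure unless a safety threshold is exceeded (systolic BP <90 or >180mmHg" mmHg). No diastolic limit is given. The next sentence allows BP to be re-checked in routine care.
- **Potential risks, detection of clinically significant problems.** "All values that reach a safety threshold (<90 or >180 systolic BP, <40 or >110 diastolic BP) will be reported" to the care provider. There is no limit by arm.
- **Protections against risk, Blood Pressure.** An average at any study visit or from home monitoring with systolic "> 180 mm Hg and/or diastolic is > 110 mm Hg will be considered an alert value" that calls for clinician assessment, and so is an average below 90 systolic or below 40 diastolic. Alerts at study visits are assessed for symptoms on the spot, in either arm. For alerts without acute symptoms, notification of the primary provider is written for "participants in the intervention group whose average SBP > 180 and DBP > 110 or SBP < 90 or DBP < 40". A later sentence, not limited by arm, says that "observation of an alert value will be communicated from the nurse as soon as possible", after which the nurse writes a record note and contacts the primary care provider.
- **Sharing of Results with Research Participants.** The nurse does not pass BP results to controls or their providers "unless they exceed the safety thresholds defined above".

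**The concern.** The systolic limits agree wherever they appear. The diastolic limits are absent from the one sentence that governs blinding. That sentence sits in the Aim 2 visit procedures, where visit staff would look first, and its bracket reads as a full definition of the threshold.

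The treating provider is named in both rules: as a blinded party in the Aim 2 procedures and as the recipient of the report under potential risks. For a reading whose only alert component is diastolic, staff cannot follow both sentences as written, and the three sites could settle the matter differently. The worse error is to withhold an alert value from the treating provider. This matters most in controls: intervention participants send home readings to the nurse, whereas controls receive a monitor only after their 12-month visit.

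The alert procedure has a related wording problem. Its notification sentence for asymptomatic alerts joins the high systolic and high diastolic limits with 'and', where the alert definition uses 'and/or', and it covers the intervention group only.

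**Working it through.** The plan states no figure to reproduce. The check is to run test readings through each rule.

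| Study-visit reading | Aim 2 blinding sentence | Potential risks | Alert definition | Asymptomatic notification sentence, read literally |
|---|---|---|---|---|
| 185/100 | blinding lifted (SBP >180) | report to provider | alert, assess | not triggered (needs SBP >180 and DBP >110) |
| 170/115 | stays blinded (SBP within 90–180) | report to provider (DBP >110) | alert, assess | not triggered |
| 120/38 | stays blinded (SBP within 90–180) | report to provider (DBP <40) | alert, assess | intervention: notify; control: not covered |

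1. In the first row the blinding sentence and the two safety sections agree. The conflict is confined to readings with SBP 90–180 and DBP <40 or >110.
2. In the second and third rows the blinding sentence and the reporting rule give opposite instructions about the same person, the care provider. The result is the same in both arms, because the assessments are defined for both.
3. Does another passage settle it? The rule on sharing results with controls defers to thresholds defined above it. Both versions are above it. The nearest are the two safety sections, which include diastolic limits, so it favours disclosure without amending the Aim 2 sentence. The later sentence on communicating an alert value, which has no arm limit, points the same way. No passage expressly reconciles the two rules.

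**How often could this arise?** The documents give no diastolic mean, SD or correlation with systolic BP, so the frequency cannot be derived from them. As an illustration only:

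- Control readings over the four visits, with 300 randomized 1:1 and the missingness in the Power section (5%, 10%, 15%): 150 × (1 + 0.95 + 0.90 + 0.85) = 555.
- Systolic BP from the Power section: mean 145, SD 17. I hold the baseline mean at every visit; the plan assumes a fall of 1 mmHg in controls by 12 months.
- Assumed, not from the documents: diastolic mean 80–90, SD 10–12, correlation 0.5–0.7, bivariate normal.
- P(90 ≤ SBP ≤ 180 and DBP <40 or >110) runs from 0.05% (80/10, correlation 0.7) through 1.55% (85/12, 0.5) to 4.2% (90/12, 0.5).
- Multiplied by 555, that is about 0.3, 8.6 and 23 readings.

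The spread comes wholly from the assumed diastolic values. These are readings, not people: one participant with repeated alerts counts more than once.

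**The case against.** The strongest reply is that this is a drafting mismatch and not two policies. The Aim 2 sentence contains its own safety exception. What it blinds is the BP outcome measure, and the outcome is systolic, so the bracket may be shorthand for that outcome. The safety sections are mandatory and not limited by arm, and the control-specific sharing rule uses the plural for thresholds already defined. On this view a control at 170/115 is assessed and reported, and withholding the value would mean ignoring several other sentences.

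Much of this stands. Disclosure does appear to be intended, and a reader should not infer that the protocol as a whole forbids reporting diastolic alerts or leaves such participants without assessment. The shorthand reading does not remove the conflict, though. The sentence refers to the in-office BP, and reporting a diastolic alert in practice discloses the reading.

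Two other inferences should be resisted.

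- The 'and' in the asymptomatic notification sentence does not mean that a reading such as 185/100 goes unreported. It is reported under potential risks, assessed as an alert, and covered by the later sentence on communicating alert values. Only one of several overlapping sentences fails to apply, probably through a slip.
- The statement that "All abnormal blood pressure results will be communicated to the clinic director at each site" does not show a breach of blinding. The context suggests alert values, and the clinic director, as such, is not among the parties that the Aim 2 sentence blinds. Defining 'abnormal' there would be an editorial choice.

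**Conclusion.** The inconsistency is real and the Aim 2 blinding sentence is wrong as written. It lifts blinding on systolic limits alone, while the safety sections require a report and an assessment for diastolic BP below 40 or above 110 mmHg as well. It covers both arms and matters most in controls. The other sections indicate that disclosure is intended, so the Aim 2 sentence is the one to change.

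Severity is minor. The conclusion rests on the text and needs no distributional assumption. The frequency of diastolic-only alerts is unknown and probably low; the illustrative range should not be quoted as an estimate. A reader might infer a bias in the systolic endpoint or a loss of power. The documents do not support that: only diastolic-only alerts are affected, and BP may be re-checked in routine care in any case.

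**What to change.** In one amendment:

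1. In the Aim 2 blinding sentence, replace the bracketed limits with: SBP <90 or >180 mmHg, or DBP <40 or >110 mmHg. The blinding, reporting, alert and results-sharing rules then use one set of limits in both arms.
2. In the asymptomatic-alert sentence under Protections against risk, change the 'and' between SBP > 180 and DBP > 110 to 'and/or', to match the alert definition.
3. In the same paragraph, state that notification of the care provider about alert values applies in either arm. Medication changes by the study team can stay limited to the intervention group.

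The cost is a few words, with no added visits, staff or data. The downside is that a few diastolic-only alerts will be disclosed to providers, which the potential-risks section already requires.

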Figure 2: Conceptual framework for the EXTRA-CVD study

of publication together.⁴³⁻⁵⁴

Conceptual Framework: Our study utilizes the RE-AIM implementation framework (Figure 2). As originally conceived by Glasgow et al⁵⁵, RE-AIM stands for **R**each **E**fficacy—**A**doption, **I**mplementation, **M**aintenance, and captures the five factors that contribute to the public health impact of an intervention. Abrams et al defined population impact as Reach X Efficacy⁵⁶, and RE-AIM added the 3 additional components to further describe contextual factors that influence the reach and efficacy of an intervention. We believe that if proven effective for ASCVD risk factor control, the concept of a prevention nurse specialist may be scaled-up to address a broad range of preventive care services for PLHIV, thus increasing its population impact. Our model may be especially relevant in the context of a changing HIV specialty workforce that will increasingly rely on non-physician providers and increased coordination with non-HIV primary care providers and specialists. Finally, the EXTRA-CVD intervention itself is grounded in two models of behavior change: (1) the information-motivation-behavioral skills model and (2) self-regulatory theory.⁵⁷⁻⁶¹ These models explain how health behavior change is mediated through self-monitoring (lifestyle change and medication adherence) and acknowledge the central role

that self-efficacy plays in sustained behavior change⁶²⁻⁶⁴ (**Figure 2 sidebar**).

4. Objectives

1. Conduct a baseline assessment of ASCVD preventive care and perceptions of ASCVD risk in the HIV specialty clinic environment. (**Aim 1**)
2. Adapt the EXTRA-CVD intervention components to the HIV specialty clinic context with key stakeholder input and data from the baseline assessments (**Sub-Aim 1.1**)
3. Evaluate the 12-month efficacy of the EXTRA-CVD intervention to improve BP and cholesterol control in PLHIV (**Aim 2**)
4. Conduct a process evaluation of the EXTRA-CVD intervention (**Aim 3**)
5. Evaluate the 12-month efficacy of an adapted virtual intervention to improve blood pressure in PLHIV

5. Hypothesis

We hypothesize that our prevention nurse-led intervention will lead to a statistically significant reduction in systolic BP (primary) and non-HDL cholesterol (secondary) over 12 months compared to those receiving general prevention education only.

6. Study Design.

Aims 1: Mixed-methods

There are two groups of participants for this aim

- **PLHIV (n=60)**

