We will conduct a process evaluation⁷² of the intervention focusing on the RE-AIM domains of ***reach, adoption, and implementation***. We will evaluate key implementation process measures across the following domains: fidelity (quality), dose delivered (completeness), dose received (exposure and satisfaction), recruitment, reach (participation rate), and context with both PLHIV and health care team participants^{73,74}

Table 3: Summary of qualitative research methods by study population		
Population	Target N	Methods
Aim 1: PLHIV	60	Focus group or interviews*
Aim 1: Healthcare Workers	36	Interviews
Aim 1.1: PLHIV Pilot participants	9	Focus group or interviews*
Aim 1.1: Feasibility Testing (Healthcare Workers)	9	Interviews
Aim 1.1: Design Team Members	20	Focus group
Aim 3: Process Evaluation (PLHIV)	30	Interviews
Aim 3: Process Evaluation (Healthcare Workers)	36	Interviews
Aim 4: Design Team Members	20	Focus group or design meeting transcripts
Aim 4: PLHIV	24	Interviews

Aim 4: Virtual Intervention Adaptation and Hybrid Implementation-Effectiveness Study**Intervention Adaptation**

The adaptation process will be similar to that described above for sub-aim 1.1, however, will be condensed into three sessions: one at-home preliminary activity and two Zoom videoconference meetings. At these meetings, several suggested virtual enhancements will be presented and design team members will engage in abbreviated exercises to (1) brainstorm, (2) conceptualize, and (3) create new virtual enhancements to the intervention. Small working groups will be assigned to further develop the enhancements into final products offline, using iterative

processes consistent with human-centered design principles

Implementation-Effectiveness Trial

In this hybrid type 3 implementation study, we will enroll (n=75) adult PLWH on suppressive ART with high BP whom are otherwise ineligible for the parent trial because they do not also have high cholesterol or because they are unwilling or unable to participate in the in-person trial. Participants will be stratified by the 3 clinic sites. Implementation outcomes based on a RE-AIM framework⁸ will be compared to parent trial participants: **reach** (% agreeing to participate), **effectiveness** (change in home systolic BP), **adoption** (frequency of home BP use), **implementation** (qualitative assessment of feasibility/acceptability), and **maintenance** (qualitative).

7. Study Enrollment and Withdrawal

Aim 1 Enrollment:

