3. Home BP monitoring. Our justification for using home BP monitoring in the EXTRA-CVD intervention is that home BP measurements are reproducible with standard deviations of less than 3.1 mmHg for both systolic and diastolic measurements⁸⁴. In addition, home BP monitors are accurate and comparable to ambulatory BP monitors⁸⁵, a ‘gold standard’ of BP measurements. Home measurements have greater predictive power for mortality as compared to office-based measurements.⁸⁶ All intervention participants will receive a home BP monitor and will be trained according to a developed protocol¹⁴ and documentation of proper usage will be recorded. Participants will use the BP monitors every day. Prior to each telephone or in-person follow-up visit, we will request BP values for the past two weeks using a standardized data collection form. Participants with poor BP control will receive nurse calls every 2 weeks, with management changes made as described in component #2 above. All intervention participants will be able to keep the BP monitor after completion of the study. Control participants will receive a BP monitor and instructions about its use after completion of the final 12-month trial visit.

Component 3—Relevant process evaluation data for aim 3: (1) Frequency of home BP checks (average checks/week and proportion of weeks with ≥ 2 checks); (2) Number and nature of medication changes in response to home BP data; (3) Barriers to home BP use; (4) Knowledge of proper home BP use.

4. EMR support tools. Evidence-based EMR tools that do not result in provider fatigue or information overload effectively improve patient outcomes^{87,88}. Our three sites use two of the most widely available EMR systems (Epic at MetroHealth/Duke and Allscripts at UH). At the UH Special Immunology Unit, there is also a parallel electronic database that may be used for clinical purposes and is amenable to programmable tools. Beginning in year 1, we will work locally with EMR (IT) support to develop these tools to assist the prevention nurse during the intervention phase:

- An extended treatment cascade graphic for the prevention-nurse specialist which will appear on his/her “dashboard” or as a recurring pdf report. During the intervention phase, the nurse will have regular access to this graphic and will receive names of specific patients who have fallen out of each cascade category.
- Tool to chart home blood pressures in EMR.

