After deeply assessing the impacts of COVID-19 through interviews conducted with EXTRA-CVD participants as described above, we will develop a virtual EXTRA-CVD hypertension intervention that will be well adapted to the post-COVID era. For this hybrid 3 implementation-effectiveness trial, PLWH participants (n=75) on suppressive ART with high BP will be enrolled in the virtually enhanced intervention. Because these subjects are otherwise ineligible for or unable to participate in the parent trial, this supplemental study arm will not poach potentially eligible participants from the parent trial. EXTRA-CVD study visits and components of the intervention will be delivered remotely, and additional remote support tools will be tailored to the HIV clinic context with assistance from the Design Team.

The purpose of this additional study is to increase the impact and scalability of the original EXTRA-CVD intervention by *assessing* the social isolation impacts of the COVID pandemic and *adapting* it to post-COVID realities in healthcare delivery. We will accomplish this goal without compromising the integrity or feasibility of the parent trial, and will thus increase the likelihood of the overall project to exert a sustained and powerful influence on the field.

Frequency of Contact

For the virtual intervention arm, after in-person written informed consent and a short visit to pick up a home BP monitor, all subsequent interactions will be conducted by telephone or videoconference, with the exception of home visits from a community health worker technology coach. Virtual follow-ups will occur at 2-weeks (Baseline), 4 months, 8 months, and 12 months.

Virtual study visits will be calculated from the date of the baseline enrollment visit in months 4, 8, and 12. Study team members should plan to schedule these visits +/- 14 days from the calculated visit date, or 21 days at the most. Visits outside of the maximum 42-day window will not be scheduled and that visit will be considered missing for that patient.

Intervention Components

The four components of the EXTRA-CVD intervention: (1) nurse-led care coordination, (2) nurse-managed medication protocols and adherence support (3) home BP monitoring, and (4) electronic medical records (EMR) support tools will be adapted to be delivered 100% virtually by telephone or videoconference, with additional supports for social isolation and technology coaching developed during the intervention adaptation phase described above.

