For the tertiary outcome of cascade category, we will calculate an ordinal four-level variable at baseline, 4, 8, and 12 months. We will use a proportional odds model fit via generalized estimating equations to examine differences over time between study arms. The proportional odds assumption will be assessed using score tests, and the model will be relaxed to partial proportional odds if necessary. Robust sandwich standard errors will be used to account for potential overdispersion and correlation among the repeated observations over time. Similarly to the primary analysis, the model will adjust for clinic site and include the same general mean model specification. The primary hypothesis will be tested via SAS PROC GENMOD to assess whether the estimated proportions in each level at 12 months differ between arms. All analyses will be conducted following an intention to treat (ITT) principle.

Missing Data:

We will assess mechanisms for missing data in this study. LMM, implicitly accommodates missingness when the response is Missing At Random (MAR); that is, when missingness is due either to treatment, to prior outcome, or to other baseline covariates included in the LMM. We will address missing data by imputing missing values using multiple imputation procedures as described by Schafer. Once missing values have been imputed, each multiply-imputed data set can be analyzed using the LMM. Final parameter estimates and their standard errors will be calculated using Rubin's formula. We will analyze our data and report final study results with and without employing the multiple imputation strategy (compared to complete case analysis) and carefully examine and describe any discrepancies found.

Power:

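### The visit-window rule has no exception or fallback for month 12, so some endpoint blood pressures go missing that could still be obtained

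*Combined protocol and SAP*

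**What the plan says.** **AAIM-High** (Aim 4 Procedures, Frequency of Contact). The schedule is: "Virtual study visits will be calculated from the date of the baseline enrollment visit in months 4, 8, and 12". The window is: "Study team members should plan to schedule these visits +/- 14 days from the calculated visit date, or 21 days at the most". Past that: "Visits outside of the maximum 42-day window will not be scheduled and that visit will be considered missing for that patient". Month 12 is treated like months 4 and 8.

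**Parent trial** (Aim 2 Procedures, under both the education control group and Frequency of contact). Visits 14 to 28 days late are done and logged as deviations. After that: "Visits outside of the +28 day window will not be scheduled and that visit will be considered missing for that patient". The COVID-19 section substitutes a window of 21 days either side for all procedures.

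**Endpoints.** The AAIM-High objective is: "Evaluate the 12-month efficacy of an adapted virtual intervention to improve blood pressure in PLHIV". Its effectiveness measure (Section 6, Aim 4) is "change in home systolic BP", reported by the participant to the nurse at the virtual visit. The parent trial's primary outcome is systolic BP at 12 months, taken in the office by a blinded assistant, and the secondary outcome is non-HDL cholesterol at the same time.

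**Home readings.** Under the home BP monitoring component, "Participants will use the BP monitors every day", and before each contact the team requests the previous two weeks of values on a standard form. AAIM-High adapts this component, and the Appendix Q checklist includes BP log sheets among the supplies.

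**Analysis.** Statistical Considerations is written around the parent-trial models: a linear mixed model, multiple imputation with results also reported without it, and "All analyses will be conducted following an intention to treat (ITT) principle". No analysis or missing-data plan is given for AAIM-High.

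**The concern.** A window that defines an on-time visit is ordinary. Here it also stops collection. If month 4 or 8 is missed, a later visit still informs the model; if month 12 is missed, nothing follows and the endpoint itself is lost. People who cannot be scheduled in time are plausibly less engaged, and their blood pressure may differ, so the loss may be selective as well as wasteful.

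The protocol's other aims point the other way. Section 7 encourages completion of all assessments and seeks post-study procedures where possible even from people who withdraw. The control-group section warns that differential loss to follow-up would threaten validity.

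AAIM-High is the clearest case. Its outcome is a home reading that may already have been taken on time when the call is late.

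**Working it through.** **1. The window.** 2 × 21 = 42 days, which matches the stated maximum.

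**2. What a late AAIM-High call could recover.** With the existing two-week form, a call 30 days after the target reaches back to day 30 − 14 = 16. Days 16 to 21 lie inside the window. The last call that still touches the window is on day 21 + 14 = 35. The current form therefore recovers the late edge of the window, not readings around the target date. Reaching those needs a longer look-back and dated entries, and the documents do not say that log entries are dated.

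**3. Parent-trial power.** Inputs from the Power section: total SD 17, within-person correlation 0.4, N = 300 (1:1), two-sided 0.05, difference 6 mmHg, and missingness of 5%, 10% and 15% at months 4, 8 and 12. The standard error (SE) of the month-12 arm effect comes from the information matrix of the stated common-intercept model, assuming compound symmetry and monotone dropout. Power = Φ(6/SE − 1.96).

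The plan's figure comes first. At 15% missing, SE = 1.94 and power = Φ(1.13) ≈ 87%, consistent with the stated >80%. The same method reproduces 15 of the 18 cells of the sample-size table within 3% or 2 patients. The other three (234, 232 and 148 stated, against 248, 244 and 138) differ by 1 to 3 power points, about 1.3 to 2.2 simulation standard errors with 1,000 datasets.

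Next, month-12 missingness is varied with months 4 and 8 held fixed:

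| Missing at month 12 | SE (mmHg) | Power for 6 mmHg |
|---|---|---|
| 15% | 1.94 | 87% |
| 20% | 2.00 | 85% |
| 25% | 2.06 | 83% |

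**4. AAIM-High precision (illustration).** The documents give no SD for home BP, so the office values are borrowed: SD of change = 17 × √(2 × (1 − 0.4)) = 18.6. The 95% half-width is 1.96 × 18.6/√n. With N = 110:

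| Loss | n | Half-width (mmHg) |
|---|---|---|
| None | 110 | 3.48 |
| 10% | 99 | 3.67 |
| 20% | 88 | 3.89 |
| 30% | 77 | 4.16 |

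The protocol also still gives n = 75 in places. There the half-width is 4.21 with no loss and 4.71 at 20%.

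**5. Possible bias (assumed inputs).** Complete-case bias in AAIM-High = share missing × difference in mean change between observed and missing participants. 10% × 5 mmHg = 0.5 mmHg; 20% × 10 mmHg = 2.0 mmHg. In the parent trial, if 5% of one arm only were lost and ran 10 mmHg above the value predicted under missing at random, the contrast would move by 0.05 × 10 = 0.5 mmHg.

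**The case against.** **Intention to treat.** A reader might infer that the rule breaks the intention-to-treat commitment. The documents do not support that. Intention to treat governs how randomised participants are analysed and does not require collection at any lag. The sentence belongs to the randomised parent trial, where the rule is the same in both arms; AAIM-High is a single arm.

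**Imputing what was refused.** A reader might also say the plan refuses a value and then imputes it. That fits the parent trial only. There the mixed model keeps each person's earlier values, and results are also reported without imputation. No imputation is planned for AAIM-High, and nothing already collected is thrown away.

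**A bounded window is defensible.** This stands in part. The model has a categorical month-12 term. Enrolment was planned from January 2021 and last visits for June 2022, so open-ended collection could measure an early participant about five months late. That is no longer a 12-month outcome, and any late period needs a limit.

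**Part of the remedy may exist.** Home values are also gathered at interim contacts, and the rule declares a visit missing without barring readings obtained elsewhere. But nothing says such readings may supply the 12-month value.

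**Size.** Home blood pressure is one of five RE-AIM outcomes in AAIM-High. Parent-trial power stays above 80% even at 25% missing. No passage shows that late attenders differ. All of this stands and limits how much weight the point can carry.

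**Conclusion.** The point holds as a cheap improvement. It is not an error or a contradiction. As written, both studies stop trying for the month-12 outcome once the window closes and name no alternative source, so some missing endpoint values are avoidable.

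The precision cost is small: about 4 points of parent-trial power between 15% and 25% missing, and about 0.4 mmHg of half-width in AAIM-High at 20% loss (3.48 to 3.89). The larger worry is selective loss. On the assumed inputs the bias runs from 0.5 to 2.0 mmHg in AAIM-High and is 0.5 mmHg in the parent trial, against a parent-trial standard error of 1.94.

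These sizes rest on an out-of-window share that the documents do not give, on office-BP variance standing in for home BP, and on the unproven premise that people who miss the window differ.

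**What to change.** - **Windows.** Keep them as the definition of an on-time visit and of a deviation.
- **Month 12 only, both studies.** Still attempt the outcome within a late period whose length is fixed in advance and without sight of outcome data. Record the actual date and include the value as the month-12 value in the main analysis.
- **AAIM-High.** Require a date on every home BP log entry. Take the 12-month value from readings dated inside the window even if the call is late, lengthening the two-week look-back as needed. State how any remaining missing 12-month values are handled.
- **Parent trial.** The remedy is a late blinded office BP and lipid draw. Home readings are not a substitute for that outcome.
- **Sensitivity analysis.** Repeat the main analysis with in-window values only.

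The cost is protocol wording, some extra scheduling and slightly more spread in the timing of the 12-month value, which the sensitivity analysis shows. The document is dated September 2022, after the June 2022 date planned for the last AAIM-High visits. If collection has closed, the use of logged readings already in hand and the AAIM-High missing-data statement can still be added.
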